#### 3.1 Enrollment

[REDACTED]  
[REDACTED]  
[REDACTED]  
[REDACTED] sixty-two (62) subjects who meet the

enrollment criteria after an Independent Physician Review using objective computer-aided imaging are required for a proper assessment of the Primary Endpoint. The study may enroll at approximately twelve (12) sites in Japan.

The Independent Physician Reviewer will assess the angiographic and IVUS core laboratory results to identify patients who will be included in the primary analysis of KAIZEN.

For a full list of criteria for subject eligibility, refer to the KAIZEN study protocol.

[figure not shown]
Roll-in subjects are considered to be initial cases by the investigator enrolled to ensure proper device training, and procedural and data collection adherence. Each investigator must complete at least one (1) roll-in. Up to three (3) roll-in subjects per Investigator (Principal Investigator and/or Sub-Investigator) are permitted. Roll-in subjects will be consented and followed per protocol, and their data will be reported separately..

## 3.2 Duration

[REDACTED]. Subject participation in the study may last about 6 months.

### 3.3 Justification of Performance Goal

[REDACTED], a rate of Acute Device Success in the KAIZEN population can be assumed to be 70%. [REDACTED]

[REDACTED] a performance goal of 50% has been defined. In other words, at least half of the subjects, who would otherwise not receive successful therapy, will benefit from orbital atherectomy.

### 3.4 Study Hypothesis

The safety and efficacy of the OAS device will be evaluated by the rate of Acute Device Success (see **Section 2.1 Primary Endpoint**) against a pre-defined success criteria of 50% (see **Section 3.3 Justification of Performance Goal**). Comparisons will be made based on the following hypothesis test:

$$H_0: \pi_s \leq 50\%$$

$$H_a: \pi_s > 50\%$$

Where:

$\pi_s$  = the probability of Acute Device Success

For the Acute Device Success endpoint, if the lower bound of the 95% confidence interval is >50%, the null hypothesis will be rejected and the endpoint will be considered met.

### 3.5 Justification of the Sample Size

A sample of 62 subjects meeting Independent Physician Review is required to reject the null hypothesis (**Table 2**). The sample size was determined based on the following:

- [REDACTED]
- Approximately 90% power
- A one-sided  $\alpha$ -level of 0.025

**Table 2 Sample Size Parameters and Justification**

Endpoint	Anticipated Performance	Performance Goal	Power	Alpha (one-sided)	Sample Size
Acute Device Success	0.70	0.5	0.90	0.025	62

Subjects who are enrolled and treated may not meet Independent Physician Review. In order to ensure a primary analysis population of at least 62 subjects, sites will need to enroll and treat patients in excess of the required 62. [REDACTED]

[REDACTED]  
[REDACTED]  
[REDACTED] Roll-in subject data will be reported separately.

**Table 3 Sample Size Parameters and Justification**

Endpoint	N	[REDACTED]	[REDACTED]
Acute Device Success	62	[REDACTED]	[REDACTED]

In order to minimize bias, a maximum of 25% of subjects may be enrolled at a single site, not including roll-in subjects. There is no minimum number of subjects required to be enrolled at each site.

## 4 DATA STORAGE

### 4.1 Raw Data Storage

The site reported and core lab data collected in the KAIZEN study will be housed in a [REDACTED]. The Clinical Events Committee (CEC) adjudication data will be housed in the [REDACTED]

[REDACTED]. Data collection for study data is performed directly by the site(s), core lab(s), and CEC through electronic representations of Case Report Forms (CRF) into tables related to each individual CRF.

## 4.2 Raw Data Exports

For analysis purposes, raw data must be extracted from the study data into a format compatible with the analysis software. Exports may be created at any time and will coincide with study milestones (e.g., 6-month endpoints) at a minimum. Data exports can consist of raw data and study metadata required to understand the export (e.g., table names, field names, and coding formats).

## 4.3 Analysis Data Sets

The raw data exports will be imported into SAS or other applicable statistical software packages for analysis. Analysis data sets will be created from the raw data in order to standardize formatting and when appropriate, create derived variables for the purpose of analysis.

## 4.4 Analysis Output

[REDACTED] Clinical Study Report Procedure outlines the process for generating output from clinical studies. CSI procedures also permit the use of external vendor standard operating procedures (SOPs) when performing statistical programming and validation. The vendor will follow their SOPs when performing any analysis external to CSI.

# 5 DATA ANALYSIS SETS

The Primary Analysis will be based on the Modified Intent to Treat (mITT) analysis set, unless otherwise noted. Enrolled subjects are those who met all of the Inclusion and none of the Exclusion criteria, signed an Institutional Review Board (IRB) approved Informed Consent Form (ICF), and had the Peripheral OAS Guide Wire enter the body (subjects are considered enrolled even if the OAD does not enter the body). [REDACTED]

[REDACTED]. The following analysis sets are specified for KAIZEN.

## 5.1 Full Analysis Set (FAS)

[REDACTED]

[figure not shown]
## 5.2 Intent to Treat (ITT) Analysis Set

## 5.3 Modified Intent to Treat (mITT) Analysis Set

## 5.4 Per Protocol (PP) Analysis Set

## 5.5 Roll-in Analysis Set

All roll-in subjects will be analyzed as part of the roll-in analysis set. The roll-in analysis set will be analyzed separately from the enrolled population.

## 6 DATA ANALYSIS METHODOLOGY & CONVENTIONS

The primary analysis of the KAIZEN clinical study subjects will be based on locked clinical data and the mITT analysis set unless otherwise noted.

Statistical analyses will be performed using [REDACTED] [REDACTED] In the event an analysis is required that is better suited for a statistical package other than [REDACTED] the other package may be used.

## 6.1 Timing of Analysis

Analyses of all primary and secondary endpoints will be performed after all FAS subjects have completed the 6-month follow-up assessment and all data have been entered and verified in the database. [REDACTED]

A horizontal bar chart with 10 categories on the y-axis and a scale from 0 to 1000 on the x-axis. The bars are black. Category 1 has the longest bar (~950). Category 2 has a very short bar (~50). Category 3 has a short bar (~150). Category 4 has a very short bar (~50). Category 5 has a medium bar (~350). Category 6 has a very long bar (~950). Category 7 has a medium bar (~350). Category 8 has a very long bar (~950). Category 9 has a medium bar (~350). Category 10 has a very long bar (~950).

Category	Approx. Number of Samples
1	950
2	50
3	150
4	50
5	350
6	950
7	350
8	950
9	350
10	950

Term	Percentage
GMOs	95
Organic	90
Natural	85
Artificial	75
Organic	70
Natural	65
Artificial	55
Organic	50
Natural	45
Artificial	35
Organic	30
Natural	25
Artificial	15
Organic	10
Natural	5
Artificial	5

## 6.3 Managing Missing Data

Although every effort will be made during study conduct to minimize missing data, missing data are expected for both general data and calculation of endpoints. The following activities may be performed to manage missing data:

## 6.4 Analysis Windows

Assessments will be made at baseline ( $\leq$  30 days prior to procedure), during the procedure, and post-procedure/discharge. Follow-up visits (analysis windows) are scheduled as office visits or phone call at the following time points post-procedure: 30-days (+14 days) and 6-months (+30 days). All windows will be calculated in days (i.e. 6-months will be calculated as 180 days).

## 6.5 Identifying Target Lesions

The protocol permits treatment of only one (1) target lesion in this study. The protocol specifies that the target lesion must be contained entirely within the protocol-defined target area (SFA and POP including P1 and P2). For the purposes of analysis, in addition to the target lesion any lesion treated with the OAD, will be considered a target lesion regardless of the protocol definition.

Endpoint data assessed on a subject-level basis requires that all success/failure criteria be assessed on all target lesions (i.e., all lesions will need to meet the specified endpoint criteria to be qualified as a success).

## 7 REQUIRED DATA ANALYSES

In cases where treatment of multiple target lesions has been performed, or treatment has been performed outside of the target area, the subject will be excluded from the PP analysis set on the basis of an inclusion or exclusion criteria deviation.

The following analyses will be performed on the populations indicated.

### 7.1 Subject Disposition

Subject disposition data will be presented on the FAS set unless otherwise noted. Tabulated data will be provided for:

The number of subjects enrolled at each site that fall into each analysis set (e.g., FAS, ITT, mITT)

Compliance to the follow-up visit schedule for subjects in the FAS and mITT analysis sets

The number and percentage of subjects by discontinuation reason

The listing of reasons will be provided for subjects excluded from the mITT and PP analysis set

### 7.2 Baseline Summary

Baseline characteristics such as subject demographics, clinical history, risk factors, and history of peripheral intervention will be summarized using descriptive statistics on the ITT and mITT analysis sets.

### 7.3 Investigator Reported Procedure, Lesion, and Treatment Summary

Site reported procedure, lesion, and treatment characteristics such as target limb characteristics, procedure time, fluoroscopy time, pre-OAD+POBA target lesion characteristics, and device usage data will be summarized using descriptive statistics on the ITT and mITT analysis sets.

### 7.4 Core Lab Assessed Data Summary

Core lab assessed IVUS and angiographic characteristics of the treated lesion at the time-points specified in the protocol (pre-procedure, post OAS+POBA, and post-procedure) such as quantitative vascular angiography (QVA) and

lesion morphology, will be summarized using descriptive statistics on the ITT and mITT analysis sets.

## 7.5 Primary Endpoint Analysis

Analysis of the primary endpoint of Acute Device Success will be assessed post-procedure and performed on the mITT analysis set. Acute Device Success is a composite endpoint comprised of:

the number of subjects with an Angiographic Core Lab assessed post OAD+POBA (and prior to the DCB) residual stenosis of  $\leq 50\%$  and,

no OAS-related severe angiographic complications defined as severe dissections (D-F), perforation, or distal emboli requiring additional treatment during the procedure as adjudicated by the CEC.

A subject is considered a success if the OAD crosses the lesion and both criteria are met. Subjects with missing data (e.g. no post-POBA imaging available) will be excluded from the primary analysis. The rate of Acute Device Success and the corresponding lower 97.5% confidence bound will be presented. The lower confidence bound of the acute device success rate will be compared against the performance goal of 50%.

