Clinically-driven target vessel revascularization (TVR)	A repeat procedure (percutaneous or surgical) performed for $\geq 50\%$ DS confirmed by angiography within all or part of the target vessel after documentation of recurrent clinical symptoms of PAD following the initial procedure.
Clinical Trial Treatment	Begins when OAS Guide Wire enters the body. Ends when the patient exits the Cath Lab.
De Novo Lesion	A native lesion not previously treated
Device Deficiency	
Inadequacy of a medical device with respect to its identity, quality, durability, reliability, usability, safety or performance
 
Note 1 to entry: Device deficiencies include malfunctions, use errors, and inadequacy in the information supplied by the manufacturer including labelling.
 
Note 2 to entry: This definition includes device deficiencies related to the investigational medical device or the comparator.
 
(per ISO 14155:2020)

Dissection classification	Type 0: None

Term	Definition															
	
Type A: Small radiolucent area within lumen of the vessel
 
Type B: Linear, non-persisting extravasation of contrast
 
Type C: Extraluminal, persisting extravasation of contrast
 
Type D: Spiral shaped filling defect
 
Type E: Persistent lumen defect with delayed ante/retrograde flow
 
Type F: Filling defect accompanied by total arterial occlusion
															
Enrolled Subjects	Subjects who met all of the Inclusion and none of the Exclusion criteria, signed an Institutional Review Board (IRB) approved ICF, and had the CSI Peripheral OAS Guide Wire enter the body.															
Enrolled and Treated Subjects	An Enrolled subject and the OAD enters the body.															
Inflow	
Arterial flow proximal to the protocol defined target area.
 
For this study, the iliac and common femoral are considered in-flow to the target area.
															

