12.2 OAD, POBA, DCB Procedure

Attempt to insert the OAD.

[figure not shown]
If the OAD cannot be inserted, the treating physician should treat the subject per standard of care and follow the subject through the 6-Month Follow-Up Visit. Refer to **Section 14** for follow-up instructions for these subjects.

If the OAD is inserted, the subject is considered **Enrolled and Treated**.

- Treat with OAD. Refer to the CSI Peripheral OAS, CSI Peripheral OAS Guide Wire, and CSI OAS Lubricant IFUs for treatment instructions.
- Refer to **Figure 1** for Solid Crown sizing to vessel size.
- Pre-dilate with uncoated PTA catheter (POBA). Refer to the appropriate device IFU for further instruction (e.g., balloon sizing, nominal pressure). The balloon diameter should be sized appropriately to the reference vessel diameter. The balloon length should correspond to the length of the area treated with OAD. Do not use high pressure balloons with nominal pressure 20 atm or greater.
 - Inflate the balloon at controlled low-pressure.
 - Continue to inflate to nominal pressure. Do not exceed nominal pressure.
 - If waist is seen at nominal pressure, recommend repeating OAD treatment (unless a complication occurs).
 - Continue inflation as needed.
- Once POBA pre-dilation treatment is complete, deploy DCB (Medtronic IN.PACT™ Admiral™). Refer to the appropriate device IFU for further instruction. (e.g., balloon sizing, nominal pressure).

Refer to **Table 7 and Appendix A** for Clinical Trial Treatment data collection and imaging requirements. Required imaging time points are described for Clinical Trial Treatment, however additional imaging per standard of care should be collected.

Figure 1: Protocol Defined Treatment Area and Crown Sizing Guide

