### 7.6.2 FAS Sensitivity Analysis

To examine the effect of subjects for whom the *CSI Peripheral Guide Wire* was inserted but the OAD was not inserted, an analysis will be performed including the enrolled subjects that were not treated with OAD as having failed the primary endpoint.

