### 7.6.3 Missing Data Sensitivity Analysis

A tipping point analysis will be performed on the mITT analysis set to assess outcomes in cases where the core lab is unable to assess outcomes due to missing or non-readable images. [REDACTED]

[REDACTED]

[REDACTED]

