### **7.7.8 Adverse Event (AE) Rates**

Adverse event rates will be assessed on a subject level for the mITT and FAS. All site reported and CEC adjudicated reportable adverse events specified in the protocol will be included in the analysis. Adverse events

are collected starting at enrollment through subject exit from the study. Adjudicated AEs will be summarized by AE term and overall for number and percent of subjects experiencing each event, and number of events.

Adverse events summaries will be provided for the time-points of enrollment to 30 days, and 31 days to study exit in the following groups:

- Serious Adverse Event (SAE): Any AE that the CEC has determined meets the protocol definition of serious
- Adverse Device Effect (ADE): Any AE the CEC has determined meets the protocol definition of related to the use of the OAS
- Serious Adverse Device Effect (SADE): Any ADE that the CEC has the protocol definition of serious
- Unanticipated Serious Adverse Device Effect (USADE): Any SAE that the CEC has determined that by its nature, incidence, severity or outcome has not been identified in the current version of the risk analysis report

Any events for which the determination of seriousness and/or relatedness to the device cannot be determined by the CEC will count as serious and/or related for the purposes of this analysis.

In addition, a subject data listing of all reportable AEs will be presented from the time of enrollment to study completion and will include the following: adverse event term, AE onset date, days to event, seriousness, relationship to OAS and procedure, outcome, and date resolved (if applicable).

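### SAP 7.5 drops subjects with missing data from the primary analysis without keeping those already known to have failed

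*SAP*

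**What the plan says.** SAP 7.5 defines success on the mITT set with three elements: "A subject is considered a success if the OAD crosses the lesion and both criteria are met". The two criteria are core-lab residual stenosis of at most 50% after OAD and POBA but before the DCB, and no OAS-related severe angiographic complication as adjudicated by the CEC. The next sentence is the missing-data rule: "Subjects with missing data (e.g. no post-POBA imaging available) will be excluded from the primary analysis". No redaction is marked in that section.

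SAP 6.3 accepts that "missing data are expected for both general data and calculation of endpoints", but the list of activities that should follow is not visible.

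Three other SAP provisions come close to the point:

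- SAP 7.6.2: "an analysis will be performed including the enrolled subjects that were not treated with OAD as having failed the primary endpoint".
- SAP 7.6.3: a tipping-point analysis on mITT "in cases where the core lab is unable to assess outcomes due to missing or non-readable images".
- SAP 7.7.8: events whose seriousness or device relatedness "cannot be determined by the CEC will count as serious and/or related for the purposes of this analysis".

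Protocol 25.4.1 has the same success rule and says nothing about missing data. That is not a conflict, because Protocol 25 leaves the detail to the SAP.

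**The concern.** When a composite needs every element to succeed, one failed element is enough to classify the subject. SAP 7.5 triggers exclusion on an absent input, not on an undetermined outcome. A subject with an adjudicated perforation, or in whom the OAD did not cross, would therefore be removed if the post-POBA image is missing.

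This combination can occur. The elements come from different sources: under Protocol 23 the CEC uses angiography and site source documents, so a complication can be adjudicated when the core lab has no readable post-POBA image. In Protocol 4, treated means only "An Enrolled subject and the OAD enters the body", so a treated subject may have an uncrossed lesion, and SAP 7.6.2 does not reach that subject. The qualifying image also belongs to one step of the procedure. A failed crossing or a complication may prevent that step, which would link the missing image to failure. That link is an inference; the documents do not state it.

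The trial has one hypothesis test, so the denominator decides the result. Two programmers could build different denominators from the present wording.

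**Working it through.** **Inputs.** Performance goal 0.50, anticipated rate 0.70, one-sided alpha 0.025, power about 0.90, n=62 (Protocol 9.1.5; SAP 3.5, Table 2). The goal is met if the lower 95% confidence limit exceeds 50% (SAP 3.4). The interval method is not visible, so exact (Clopper-Pearson) and score (Wilson) bounds are both shown.

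**The plan's own figure.** With the normal approximation, n = [(1.960×√(0.5×0.5) + 1.2816×√(0.7×0.3))/0.2]² = 61.41, rounded up to 62, with power 0.903. The stated sample size reproduces. The exact test at n=62 needs 40 successes and has power 0.860.

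**Step 1: lower bounds near the threshold.**

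| Successes/n | Exact | Score |
|---|---|---|
| 39/62 | 0.4969 | 0.5046 |
| 39/61 | 0.5063 | 0.5139 |
| 38/62 | 0.4807 | 0.4885 |
| 38/61 | 0.4896 | 0.4975 |
| 38/60 | 0.4990 | 0.5068 |

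With the exact bound, dropping one known failure turns 39/62 from a miss into a pass. With the score bound, 39/62 already passes, and two drops are needed to turn 38/62 into a pass. These outcomes are uncommon: at a true 70%, exactly 39 successes of 62 has probability 5.1% and exactly 38 has 3.6%.

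**Step 2: a fixed number d of known failures dropped, nothing else missing, true rate 50%.** The false-pass probability is P(X ≥ critical value at n=62−d), with X ~ Bin(62, 0.5). The critical values for n = 62, 61, 60, 59 are 40, 39, 39, 38 (exact) and 39, 39, 38, 38 (score).

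| d | Exact | Score |
|---|---|---|
| 0 | 1.5% | 2.8% |
| 1 | 2.8% | 2.8% |
| 2 | 2.8% | 4.9% |
| 3 | 4.9% | 4.9% |

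**Step 3: successes lose images too (assumed shares).** Take a true rate of 50%, with 10% of all subjects failing on crossing or complication. Images are missing in 5% of the other subjects and in a share r of those failures. The dropped share is 0.9×0.05 + 0.1×r, and the success probability among those kept is 0.5×0.95/(1 − dropped share). The critical value is recomputed at each n.

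| r | Dropped share | Success probability kept | False pass, exact | False pass, score |
|---|---|---|---|---|
| 5% | 0.050 | 0.500 | 1.8% | 2.3% |
| 20% | 0.065 | 0.508 | 2.5% | 3.2% |
| 50% | 0.095 | 0.525 | 4.4% | 5.6% |

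If known failures are kept, the excluded share is 0.9×0.05 = 0.045 whatever r is. The success probability is 0.475/0.955 = 0.4974, and the false-pass probability is 1.6% (exact) or 2.1% (score) in all three rows.

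**Step 4: cost of keeping known failures when images are missing independently of outcome.** Take a true rate of 70% and 5% of images missing.

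| Rule | Expected rate | Power, exact | Power, score |
|---|---|---|---|
| Current | 70% | 0.857 | 0.880 |
| Keep failures, 10% fail on crossing or complication | 0.665/0.955 = 69.6% | 0.843 | 0.868 |
| Keep failures, 20% fail on crossing or complication | 0.665/0.960 = 69.3% | 0.829 | 0.856 |

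**The case against.** The strongest reply is that the controlling text cannot be seen. The SAP 6.2 conventions, the SAP 6.3 list, the mITT definition and the details of 7.6.3 are redacted or not shown, and a rule for partly known composites could sit in any of them. This stands: the finding is that 7.5 does not say, not that the plan has no rule.

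A second reply is that missing data can mean that the composite is undetermined, in which case a known failure is not missing at all. That reading is possible. The text does not state it, however, and its example points the other way.

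Third, the link from failure to a missing image is thin. The phrase in Protocol 12.2, "recommend repeating OAD treatment (unless a complication occurs", governs repeat OAD and does not say that POBA or its angiogram is skipped. Table 7, note 11 requires images at every Appendix A time point. If the guide wire does not cross, the OAD is not used and 7.6.2 applies. The group at issue is therefore narrow and its size is not given. All of this stands, but the literal rule misclassifies a known failure whatever the reason for the missing image.

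Fourth, the false-pass figures depend on assumed shares. With the exact bound, a fourfold difference in missingness (20% against 5%) only brings the error to 2.5%. Part of the score excess comes from the interval, which already gives 2.8% with nothing missing. If missingness is independent of outcome, the current rule is unbiased and the alternative is slightly conservative. These points limit the size of the concern.

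Finally, the tipping-point analysis and the separate reporting of complications (7.7.5) would expose a fragile result. They would not change the primary decision.

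**Conclusion.** The concern holds and should be fixed, with medium confidence. Followed as written, SAP 7.5 can remove a treated subject already known to have failed on crossing or complication, and no visible provision restores that subject to the primary analysis. Compared with keeping known failures, any resulting error favours meeting the goal.

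The practical size is uncertain. One dropped failure (exact bound) or two (score bound) can reverse a result at the threshold, but such results are uncommon at the anticipated rate. A clear excess of false passes requires images to be missing considerably more often in subjects who failed than in the rest. The documents give no missing-image rate, so every share used above is an assumption.

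**What to change.** Replace the exclusion sentence in SAP 7.5 with:

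> A subject with any element of Acute Device Success known to have failed (OAD did not cross, core-lab residual stenosis >50%, or CEC-adjudicated OAS-related severe angiographic complication) is a failure and remains in the denominator, whatever other data are missing. Only subjects with no failed element and at least one undetermined element (stenosis, crossing or CEC adjudication) are missing; they are excluded from the primary analysis and included in the tipping-point analysis (7.6.3).

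Widen the visible scope of 7.6.3 to match, since it names only core-lab images. The 7.7.8 rule for events the CEC cannot classify is confined to the AE analysis, so 7.5 needs its own statement. Report how many subjects fall in each group. If text not visible here already contains this rule, a cross-reference from 7.5 is enough.

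The change is to wording in 7.5 and 7.6.3 and uses data already collected. Its statistical cost is the small loss of power shown in Step 4, which arises if images are missing independently of outcome.
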